4.1.2 FVIII Incremental Recovery

If FVIII levels resulting from endogenous FVIII production from transduced hepatocytes begin to decline without evidence of elevation of transaminases, the participant will be evaluated for evidence of anti-FVIII antibody formation. This evaluation will include FVIII inhibitor assays and FVIII incremental recovery with blood sample collection consistent with the Investigator's clinical practice after receiving 50 IU/kg of FVIII product. Blood sampling will be done at appropriate time-points to enable acceptable determination of PK parameters (Iorio, 2016).

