3.4 Secondary Endpoints

The secondary endpoints include the following:

- Additional kinetic assessments including, but not limited to:
 - Time to achieve steady-state FVIII activity levels;
 - Vector-shedding of SPK-8016 in bodily fluids.
- Incidence of immune responses to AAV capsid protein and BDD-hFVIII transgene.

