ALT levels and extinguished the ELISpot signal in all cases. Two of the 5 participants who received corticosteroids in the 2×10^{12} vg/kg dose group, however, showed loss of transgene expression likely due to the immune response. Both of these individuals eventually returned to hemophilia prophylaxis regimens, one with recombinant FVIII, the other with emicizumab. Given that 5 of 7 participants in the 2×10^{12} vg/kg group required corticosteroids, including 2 participants who lost FVIII expression, the institution of a consistent, standardized short course of prophylactic corticosteroids appeared warranted in an attempt to pre-emptively manage potential immune responses. In the first 2 participants administered SPK-8011 at 2×10^{12} vg/kg using prophylactic oral corticosteroids (1 mg/kg or 60-80 mg), the first was started on corticosteroids on Day 27 due to falling FVIII and the second was started on Day 26 due to rising ALT and decreasing FVIII expression. In both of these participants, early initiation of corticosteroids resulted in a transient supraphysiologic increase in FVIII levels to greater than 200%. An intermediate dose cohort (1.5×10^{12} vg/kg) was initiated. Reduction of the vector genome dose was successful in terms of avoiding supraphysiologic levels of FVIII upon initiation of corticosteroids, but in all participants where corticosteroids have been started prior to 6 weeks post vector infusion, tapering off has been challenging, and consequently, prolonged courses have been required, with associated steroid related side effects. [REDACTED]

[REDACTED] Because of the prolonged steroid taper when steroids were administered beginning at 4 weeks, which was not observed with later initiation of steroids, prophylactic steroids will be avoided going forward.

Based on discussions with expert immunology consultants, the Sponsor proposes to again investigate administration of steroids only in response to one of the previously described triggers, i.e., declining FVIII levels or rising transaminases, [REDACTED]

[REDACTED] Oral corticosteroids may be utilized, if clinically indicated. ELISpot is an exploratory assay and not predictive as a trigger for immunomodulation.

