4.1.3.1 Corticosteroid Regimen

If transaminases become elevated or the FVIII declines, [REDACTED]

[REDACTED]

[REDACTED]

[REDACTED]. Treatment will continue until resolution of the immune response occurs and may require the use of additional immunomodulatory agents. Daily oral corticosteroids given in a tapering dose regimen may be utilized instead of [REDACTED] corticosteroids, if in the estimation of the Investigator an oral dosing regimen is clinically indicated. The Investigator in collaboration with the Sponsor will have flexibility in implementing the corticosteroid regimen, since the exact regimen and course will depend on clinical circumstances.

If reactive corticosteroids [REDACTED] or oral dosing) are triggered by an apparent immune response, additional blood samples for “Immune Profiling” (cytokines) and “PAX gene” should be collected 1) prior to the initiation of corticosteroids (if this is possible without delaying the initiation of corticosteroid therapy) and 2) at 1 week (± 2 days) and at 2 weeks (± 2 days) following the first dose of corticosteroids. At the discretion of the Investigator, nucleic acid amplification testing (NAAT) for infection with SARS-CoV-2 (the infectious agent in COVID-19) may be performed at this time for individuals who do not have symptoms consistent with upper or lower respiratory tract infection or COVID-19. NAAT testing should be performed at

this time for individuals with any of the following symptoms: cough, shortness of breath or difficulty breathing, fever, chills, sore throat, new loss of taste or smell; new persistent/recurrent muscle pain or headache. For individuals who do not have any of these symptoms, the initiation of reactive corticosteroids should not be delayed pending results of NAAT testing. For individuals who do display any of these symptoms, initiation of corticosteroids may be delayed at the discretion of the Investigator until after results of NAAT testing are known. Note: The Infectious Disease Society of America panel suggests collecting nasopharyngeal, or mid-turbinate or nasal swabs rather than oropharyngeal swabs or saliva alone for SARS-CoV-2 RNA testing in symptomatic individuals with upper respiratory tract infection (URTI) or influenza like illness (ILI) suspected of having COVID-19.

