4.1.3.4 Experience with Long Term Immunomodulation

There is extensive experience with corticosteroids and immunosuppressive regimens in hemophilia: first, as a maneuver to eradicate antibodies to factor VIII or IX, clinically termed inhibitors (Nilsson, 1976; Hultin, 1976; Hay, 2006) and second, in the setting of liver transplantation due to the high prevalence of hepatitis C among adults with haemophilia (Gordon, 1998; Wilde, 2002). Many individuals with hemophilia have been maintained on standard liver transplant immunosuppression regimens for years. Corticosteroids have been used to treat people with asthma, idiopathic thrombocytopenic purpura, organ injury from autoimmune diseases including autoimmune hepatitis and systemic lupus erythematosus nephritis and lupus CNS manifestations, and other medical conditions. For participants with severe hemophilia A, the benefit of long-term expression of a modest level of clotting factor far outweighs the risk of receiving a course of corticosteroids or other immunomodulatory agents.

The long-term side effects of the immunomodulatory drugs expected to be used in this study are well-characterized. Participants who develop immune hepatitis will be monitored closely to minimize the risk of the side effects. Pulse dosing of steroids has been shown to be efficacious in reducing an immediate immune response with a reduction in corticosteroid related adverse events (when compared to daily high dose oral corticosteroids) in several autoimmune diseases (Fanouriakis, 2019; Gordon, 2018; Wei, 2016). The use of oral prednisone in [REDACTED] may reduce the reactivation of the inflammatory process or

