6.8 Follow-up Observation Period (Weeks 1-52)

Visits during the follow-up period may occur at either the vector-administration or follow-up center. Any visit requiring a physical exam must be performed at the study center. All other visits without a physical exam may be performed by a qualified and trained in-home service provider.

U.S. Centers for Disease Control and Prevention (CDC) guidance on hygiene, travel, and social interactions will be considered by the Investigator and Sponsor to minimize the risk of community acquired viral infections. This may include recommending a shelter in place and/or other social distancing measures during immunomodulation. *FDA Guidance for Industry, Investigators, and Institutional Review Boards on Conduct of Clinical Trials of Medical Products during COVID-19 Pandemic (2020)* will provide considerations to assist in assuring the safety of trial participants. International and local health guidelines may be observed for sites outside of the United States.

6.8.1 Days 3, 7, 10, 14, 17, 21, 24, 28, 31, 35, 38, 42, 45, 49, 52, 56, 59, 63, 66, 70, 73, 77, 84 (± 2 days)

A minimum of twice weekly visits is required from Weeks 1-11 to monitor for a potential rise in hepatic transaminases and/or loss of FVIII transgene expression. Visits at Weeks 1-11 may be performed by an in-home service provider.

If an apparent immune response/liver inflammation is observed and triggers the initiation of reactive corticosteroids, additional samples are to be collected for Immune Profiling and PAX Gene prior to corticosteroid administration, if possible, and then Week 1 (± 2 days) and Week 2 (± 2 days) following initiation of corticosteroids (see Table 1 and Section 4.1.3.1).

If immunomodulation is initiated, weekly visits should continue to collect transaminases, FVIII (local and central lab), Immunology. Weekly hematology and monthly lipid profile results should also be monitored locally for Cohorts 1 and 2 until [REDACTED] dosing has stopped, and this may be altered based on clinical response. Social distancing may be recommended for the duration of immunomodulation.

The following procedures will be performed at all visits unless otherwise noted:

- Perform physical examination, including weight (*Days 3, 49, 84*)
- Measure vital signs (*Days 3, 49, 84*)
- Hemophilia Activities List, Health Economic Assessment (*Days 49 and 84*)
- Review FVIII Infusion Log (*Days 49, 84*)

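### In the readable text no for-cause FVIII inhibitor test is specified when FVIII falls together with raised transaminases, and the first scheduled post-vector test (Day 49) follows the Weeks 3-6 steroid starts seen in this study

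*Protocol*

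**What the plan says.** Protocol Section 4.1.2 contains the only event-driven inhibitor work-up in the readable text. It applies when vector-derived FVIII levels "begin to decline without evidence of elevation of transaminases, the participant will be evaluated for evidence of anti-FVIII antibody formation". Its content is then given: "This evaluation will include FVIII inhibitor assays and FVIII incremental recovery". No timing relative to steroid treatment is stated.

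Section 4.1.3 gives the triggers for reactive steroids as "i.e., declining FVIII levels or rising transaminases".

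Once steroids are triggered, Section 4.1.3.1 says that "additional blood samples for “Immune Profiling” (cytokines) and “PAX gene” should be collected 1) prior to the initiation of corticosteroids", and again at one and two weeks. SARS-CoV-2 testing is optional at this point, or recommended for men with symptoms. Table 1 footnote 32 and Section 6.8.1 name the same two research samples; in 6.8.1, "additional samples are to be collected for Immune Profiling and PAX Gene prior to corticosteroid administration, if possible". For the period on treatment, 6.8.1 adds: "If immunomodulation is initiated, weekly visits should continue to collect transaminases, FVIII (local and central lab), Immunology". Table 3 defines Immunology as PBMC assays and places the FVIII inhibitor under Coagulation, so the weekly set does not include it.

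Scheduled inhibitor tests after vector are on Days 49 and 84 (6.8.1) and Weeks 14, 26, 40 and 52 (6.8.2), whatever the transaminases.

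Section 3.4 makes the following a secondary endpoint: "Incidence of immune responses to AAV capsid protein and BDD-hFVIII transgene". SAP Section 1.1.2 keeps the immune response to the transgene product as a secondary objective, and Protocol Section 9.1.3 lists adverse events associated with inhibitor formation as of special interest.

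**The concern.** When FVIII falls after gene transfer, two explanations compete: a cellular response that removes transduced hepatocytes, or an antibody against FVIII itself. The plan looks for the second only when transaminases are not raised. When both signals are present it goes to corticosteroids, and the samples it asks for beforehand cannot show an inhibitor.

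The order matters because Section 4.1.3.4 describes corticosteroids and immunosuppressive regimens as having been used in hemophilia "first, as a maneuver to eradicate antibodies to factor VIII or IX, clinically termed inhibitors". A test taken only after steroids have begun is weaker evidence that no inhibitor was present when FVIII fell. Two things depend on it: the transgene immune-response endpoint, where a finding of no inhibitors would carry less weight, and the attribution of FVIII loss to a capsid response. The study is also meant to inform later work in men with inhibitors.

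**Working it through.** The plan states no figure on this point to reproduce. The check compares the triggers and then the visit calendar.

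**Step 1: triggers side by side**

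| Signal | Reactive steroids may start (4.1.3, 4.1.3.1) | For-cause inhibitor work-up (4.1.2) |
|---|---|---|
| FVIII falls, transaminases not raised | Yes | Yes |
| Transaminases raised, FVIII not falling | Yes | No |
| Both | Yes | No |

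The third row is the gap. The combination is expected: Section 4.1.3 describes it among the patterns that prompted prednisone in this study. It also reports a sister-study participant who started steroids on Day 26 for rising ALT with decreasing FVIII.

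**Step 2: scheduled tests**

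- Follow-up visits listed: 23 in 6.8.1 and 10 in 6.8.2, 33 in all.
- Visits with an inhibitor test: Days 49 and 84, and Weeks 14, 26, 40 and 52 (Days 98, 182, 280 and 364). That is 6 of 33.
- Thirteen visits, Days 3 to 45, come before Day 49. None has an inhibitor test.
- Intervals between tests: 84 - 49 = 35, 98 - 84 = 14, 182 - 98 = 84, 280 - 182 = 98 and 364 - 280 = 84 days.

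**Step 3: steroid starts against that calendar** (taking week w as Day 7w)

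- This study, Weeks 3-6 (Section 4.1.3): Days 21 to 42, all before Day 49. Time on steroids at the first post-vector test is 49 - 42 = 7 to 49 - 21 = 28 days. With the ±2-day visit window it is 47 - 42 = 5 to 51 - 21 = 30 days.
- The last earlier result is from screening, which may run to 16 weeks (112 days). If drawn at the start of screening, it is 112 + 21 = 133 to 112 + 42 = 154 days old when steroids start.
- Sister-study participant at Day 26: 49 - 26 = 23 days before the first post-vector test on this calendar.
- Sister study at 2×10^12 vg/kg, starts at 6 to 11 weeks (Days 42 to 77): starts on Days 42-48 have no earlier post-vector test. Starts on Days 49-77 have one that is 0 to 77 - 49 = 28 days old.

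**Step 4: later scheduled tests as a substitute**

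Prednisone courses in this study ran 43-48 weeks (Section 4.1.3). The earliest possible end is Week 3 + 43 = Week 46. On the present calendar, the tests from Day 49 through Week 40 (five of the six) would fall during such a course. The amendment aims to shorten steroid exposure, so this describes past experience and is not a forecast.

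**Step 5: archived plasma as a substitute**

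Section 6.2.6 provides for spare plasma at every FVIII draw, which would cover every visit in 6.8.1. Section 6.8.1 itself lists spare plasma only at Day 84. Section 2.3.1.2 keeps archives for analysis if an inhibitor develops, which presupposes that one has been detected. No passage in the readable text prompts testing of stored plasma from before steroids.

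**The case against.** The strongest reply is that the gap is narrow and partly unverifiable. Several lines of 4.1.3.1 are redacted just after the triggers are named, and the Table 1 grid and its first footnotes are not in the text, so an inhibitor test could stand there. Footnote 22 also permits unscheduled safety tests. This stands as a limit on certainty, but every readable list of pre-steroid and on-treatment samples omits the assay.

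Section 4.1.2 can also be defended as a sensible differential: raised transaminases already point to a hepatocyte-directed response. Participants have more than 150 exposure days and no measurable inhibitor at entry, and no inhibitors have been reported in this study or the sister study. That makes an inhibitor unlikely, but the endpoint still has to be ascertained in the men in whom immune activation is most evident.

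Several stronger readings are tempting, and the documents do not support them:

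- **That men with both signals go untested.** Six scheduled tests apply to everyone. From Day 49 on, a man starting steroids has had at least one post-vector test, though not one prompted by the signal.
- **That the protocol says steroids eradicate inhibitors.** It says such regimens have been used for that purpose. It does not say that they reliably succeed, or within 7 to 28 days.
- **That 3 of 4 men fell in the gap.** Three of 4 had an apparent immune response that prompted steroids, but the triggers included ELISpot, which no longer counts, and the description uses an and/or. Section 2.3.1.3 reports no related transaminitis adverse events among the four. Section 4.1.2 does not define elevation, so the number with both signals cannot be derived.
- **That the suspension rule in Section 4.3 is undermined.** It names an inhibitor that is confirmed and persistent. The risk here is a transient one.

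**Conclusion.** The point holds in limited form. In the readable text, no inhibitor test is prompted when FVIII falls with raised transaminases. A man with both signals who starts steroids at Weeks 3-6 has no post-vector inhibitor result from before steroids. On that timing the first result comes 7 to 28 days into treatment. For starts from Day 49 to Day 77 the weakness is smaller: a scheduled result up to 28 days old exists.

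The consequence is possible under-ascertainment of a transient inhibitor, and FVIII loss attributed to a capsid response without the alternative having been examined. It cannot be expressed as a rate: the true inhibitor frequency and the share of men with both signals are unknown, so a claim that incidence is biased by a given amount would be unsupported.

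The conclusion assumes that the redacted part of 4.1.3.1 and the missing Table 1 content add no inhibitor test. It also takes Weeks 3-6 as relevant timing. Those starts were seen at 5×10^11 vg/kg, before the two prophylactic immunomodulation cohorts and with ELISpot as a trigger, so later starts may differ.

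**What to change.** Add a central FVIII inhibitor assay (Nijmegen-Bethesda, already in Table 3) to the pre-corticosteroid sample set in Section 4.1.3.1, Table 1 footnote 32 and Section 6.8.1, under the condition those places already set: drawn if possible, without holding up steroids. Reconcile Section 4.1.2 with these passages, so that inhibitor sampling does not depend on whether transaminases are also raised; the incremental-recovery study can stay as it is. If the redacted text or the Table 1 grid already specifies this test, a cross-reference from 4.1.2 is enough.

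The cost is one extra assay per steroid start, on a draw already planned, plus a short amendment and a laboratory-manual line. No dose, trigger or treatment rule changes. One limit remains: in Cohorts 1 and 2 immunomodulation starts before vector, so the added sample would precede corticosteroids but not all immunosuppression, and should be reported as such.

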4.1.3 Corticosteroids

Based on observation and experience from earlier clinical studies of liver-directed AAV gene transfer, including the SJ-UCL trial (Nathwani, 2011b; Nathwani, 2014), the Sponsor's earlier clinical studies [REDACTED], and the Baxalta BAX 335 trial (NCT#01687608), participants may develop an immune response to the vector capsid, as evidenced by a transient rise in transaminases (AST and/or ALT) and/or a loss in FVIII activity in the peripheral blood, as measured by IFN-gamma ELISpot (Manno, 2006; Mingozzi, 2007; Nathwani, 2011b). In the Sponsors' similar gene therapy trial, SPK-8011, 12 participants have required corticosteroids following vector infusion. Two participants in the low dose cohort, 5×10^{11} vg/kg, did not mount an immune response. Two of the 3 participants in the second dose cohort, 1.0×10^{12} vg/kg, received corticosteroids starting at 5 and 11-weeks post vector infusion; a declining FVII level was the trigger. Of the 7 initial participants treated in the third dose cohort with 2×10^{12} vg/kg SPK-8011, 5 required corticosteroids, starting at 6 to 11-weeks post vector infusion for 1 or more of the following triggers: declining FVIII levels, rise in ALT above participant baseline or elevated IFN- γ ELISpots to AAV capsid. Steroid initiation normalized

ALT levels and extinguished the ELISpot signal in all cases. Two of the 5 participants who received corticosteroids in the 2×10^{12} vg/kg dose group, however, showed loss of transgene expression likely due to the immune response. Both of these individuals eventually returned to hemophilia prophylaxis regimens, one with recombinant FVIII, the other with emicizumab. Given that 5 of 7 participants in the 2×10^{12} vg/kg group required corticosteroids, including 2 participants who lost FVIII expression, the institution of a consistent, standardized short course of prophylactic corticosteroids appeared warranted in an attempt to pre-emptively manage potential immune responses. In the first 2 participants administered SPK-8011 at 2×10^{12} vg/kg using prophylactic oral corticosteroids (1 mg/kg or 60-80 mg), the first was started on corticosteroids on Day 27 due to falling FVIII and the second was started on Day 26 due to rising ALT and decreasing FVIII expression. In both of these participants, early initiation of corticosteroids resulted in a transient supraphysiologic increase in FVIII levels to greater than 200%. An intermediate dose cohort (1.5×10^{12} vg/kg) was initiated. Reduction of the vector genome dose was successful in terms of avoiding supraphysiologic levels of FVIII upon initiation of corticosteroids, but in all participants where corticosteroids have been started prior to 6 weeks post vector infusion, tapering off has been challenging, and consequently, prolonged courses have been required, with associated steroid related side effects. [REDACTED]

[REDACTED] Because of the prolonged steroid taper when steroids were administered beginning at 4 weeks, which was not observed with later initiation of steroids, prophylactic steroids will be avoided going forward.

Based on discussions with expert immunology consultants, the Sponsor proposes to again investigate administration of steroids only in response to one of the previously described triggers, i.e., declining FVIII levels or rising transaminases, [REDACTED]

[REDACTED] Oral corticosteroids may be utilized, if clinically indicated. ELISpot is an exploratory assay and not predictive as a trigger for immunomodulation.

In this SPK-8016-101 study, 4 participants have received SPK-8016 at dose level 5×10^{11} vg/kg. Three of the 4 participants developed an apparent immune response to the AAV capsid, characterized by transient elevations in liver transaminases and a decrease in FVIII expression, and/or persistent positive IFN- γ ELISpot results to the [REDACTED], which have prompted initiation of corticosteroid therapy (prednisone). Prednisone was started week 3-6 post infusion. Prolonged tapering of daily oral corticosteroids has been required in all participants (total courses of 43-48 weeks prednisone) to avoid and treat late recurrences of apparent hepatocyte-targeted immune response. [REDACTED]

[REDACTED]

[REDACTED]

[REDACTED]

[REDACTED]

[REDACTED]

[REDACTED]

[REDACTED]

[REDACTED]

[REDACTED]

[REDACTED]

Significant elevations of transaminases (≥ 5 - 10 x ULN) will be treated as a safety issue and appropriate medical care will be instituted according to the standard of care of the medical facility involved.

Based on the data observed to date in this trial as well as in Hemophilia B trials (Manno, 2006; Nathwani, 2014), a course of corticosteroids may be initiated in participants, depending on the clinical judgement of the Investigator and in consultation with the Sponsor, after a trigger is identified in the transaminases or FVIII post vector transfusion and may be continued in a pulse or tapering regimen, IV and/or oral, until clinical concern of hepatic inflammation is resolved and per Investigator/Sponsor discretion. The ELISpot assay is considered exploratory and not a predictive trigger for reactive immunomodulation.

